7.3.2 Serological Immunogenicity Endpoint Assays

Blood samples for immunogenicity assessments will be collected before administration of study treatment. The following analytes will be measured:

- Serum bAb levels against SARS-CoV-2 as measured by ligand-binding assay specific to the SARS-CoV-2 S protein
- Serum bAb levels against SARS-CoV-2 as measured by ligand-binding assay specific to the SARS-CoV-2 nucleocapsid protein
- Serum nAb titer against SARS-CoV-2 as measured by pseudovirus and/or live virus neutralization assays

Serum will be tested using the ligand-binding assay specific to the SARS-CoV-2 nucleocapsid to determine the immunologic status of study participants at baseline and assess for seroconversion due to infection during the course of the study. Serum from a subset of participants will be tested in the other assays. The selection of the subset and timepoints to be tested are described in the statistical analysis plan. Sample aliquots will be designed to ensure that backup samples are available and that adequate vial volumes may allow for further testing.

The date of each sample collected will be recorded in the eCRF, and unique sample identification will be used to maintain the blind at the laboratory at all times and to allow for automated sample tracking and storage. Handling and preparation of the coded samples for analysis, as well as shipping and storage requirements, will be provided in a separate study manual.

The ligand-binding assay and measurement of nAb titers will be performed in [name] Lab, NIH.

7.3.2.1 Endpoint Assay Biospecimen Collection for Vaccine-Naïve Cohorts

| Test/Assay | Volume blood** (approx) | Type of tube** | Collection point* | Location of specimen analysis |
|---|----------------------------|-------------------|---|-------------------------------------|
| Serological Immunogenicity Assays | 5-10 mL (for plasma) | EDTA | D1, 29, 36, 57, 394, at COVID-19 infection*** | NIH [name] Lab |
| Neutralization assay using a wild-type SARS-CoV-2 | 3 mL (for serum) | SST | D1, 29, 36, 57, 209, 394, at | |

| Test/Assay | Volume blood** (approx) | Type of tube** | Collection point* | Location of specimen analysis |
|------------|----------------------------|-------------------|--------------------------|-------------------------------------|
| | | | COVID-19 infection*** | |

* See study calendar for collection windows. Sample collection should occur prior to vaccine administration on applicable days (i.e., D1 and D29). Participants who opt to receive a booster vaccine will have their samples drawn according to the Booster Vaccine Cohort calendar.

**Tubes/media may be adjusted at the time of collection based upon materials available if approved by the PI/laboratory investigator

***If a participant tests positive for COVID-19 while on study these labs will be collected within 2 weeks of a positive PCR test. A second post-infection blood collection will occur 2-4 weeks after this initial blood draw. These post-infection blood draws are optional.

7.3.2.2 Endpoint Assay Biospecimen Collection for Booster Vaccine Cohorts

| Test/Assay | Volume blood** (approx) | Type of tube** | Collection point* | Location of specimen analysis |
|---|----------------------------|-------------------|---|-------------------------------------|
| Serological Immunogenicity Assays | 5-10 mL (for plasma) | EDTA | D1, 8*, 29, 57, 180, 360, at COVID-19 infection*** | NIH [name] Lab |
| Neutralization assay using a wild-type SARS-CoV-2 | 3 mL (for serum) | SST | D1, 8*, 29, 57, 180, 360, at COVID-19 infection*** | |

* See study calendar for collection windows. Sample collection should occur prior to vaccine administration on applicable days (i.e., D1 and D29). D8 assessments are optional except for CAR T Cell Cohort.

**Tubes/media may be adjusted at the time of collection based upon materials available if approved by the PI/laboratory investigator

***If a participant tests positive for COVID-19 while on study these labs will be collected within 2 weeks of a positive PCR test. A second post-infection blood collection will occur 2-4 weeks after this initial blood draw. These post-infection blood draws are optional.

7.3.3 Salivary Assessments

7.3.3.1 Salivary measurement of IgG antibodies against the SARS-CoV-2 nucleocapsid and spike proteins

The luciferase immunoprecipitation systems (LIPS) immunoassay was used to study IgG antibody response against SARS-CoV-2 in saliva. Due to the potential biohazard of infectious SARS-CoV-2 in saliva and a viral inactivation protocol involving heating saliva at 56°C for 30 minutes was employed. For these SARS-CoV-2 antibody measurements, Renilla luciferase-nucleocapsid and Gaussia luciferase-spike fusion protein extracts were employed with protein A/G beads as the IgG capture reagent as previously described [39]. Due to the lower levels of immunoglobulin present in saliva, 10 ml of each saliva sample was utilized in the LIPS assay as previously described [40].

Known SARS-CoV-2 serum samples for IgG antibodies against nucleocapsid and spike proteins and saliva from uninfected controls were used for assigning seropositive cut-off values and for standardization.

- **Saliva collection procedure:**

Participants are asked to refrain from eating or drinking 90 minutes before their appointment but are encouraged to maintain adequate hydration the day before the appointment. To collect saliva, 50mL sterile falcons are used as saliva receptacles. We ask that participants relax with their head slightly forward and to refrain from swallowing for 2-4 minutes. Participants should place their lips up to the orifice of the 50 mL falcon (“kiss the opening”) and push/squeeze the saliva that pools in the floor of their mouth into the orifice of the 50 mL falcon. Participants will be asked to expectorate every 30 seconds for 2-5 minutes. Ideally, 2-4 mL of saliva should be collected.

- **Saliva specimen processing:**

Saliva (1mL) can be transferred to individual 2.0 mL screw-top conical tubes (Sarstedt 2.0 screw cap vials preferred) using a P1000 pipet or a sterile transfer pipet (actual volume can vary significantly). This would be 2-3 tubes/participant. These tubes should be stored frozen at -80C for long term storage.

7.3.3.2 Additional assays

Saliva samples will be used for additional research, in particular whole or targeted high throughput genome sequencing and its use in the analysis of immune system modulating genomic loci such as the IGHV region and the KIR region

7.3.4 Immune Assessments by the NCI LTIB Lab

The following immune assays be performed at the Laboratory of Tumor Immunology and Biology (LTIB) at the NCI's Center for Cancer Research (CCR) and include flow cytometry-based and serum assays.

Studies may be performed in select participants where adequate samples are available:

Peripheral blood mononuclear cells (PBMCs)

- PBMCs may be analyzed for changes in standard immune cell types (CD4 and CD8 T cells, natural killer [NK] cells, regulatory T cells [Tregs], myeloid-derived suppressor cells [MDSCs], and dendritic cells) as well as over 120 immune cell subsets, as described elsewhere [41, 42]
- PBMCs from selected subjects may be analyzed for function of specific immune cell subsets, including CD4 and CD8 T cells, NK cells, Tregs, and MDSCs.
- PBMCs may be analyzed for immune responses against SARS Co-V2 using an intracellular cytokine staining assay. PBMCs will be stimulated *in vitro* with overlapping 15-mer peptide pools encoding proteins of SARS Co-V2 (e.g., spike glycoprotein, nucleoprotein); control peptide pools will involve the use of human leukocyte antigen peptide as a negative control and CEFT peptide mix as a positive control. CEFT is a mixture of peptides of CMV,

Epstein-Barr virus, influenza, and tetanus toxin. Post-stimulation analyses of CD4 and CD8 T cells will involve the production of IFN- γ , IL-2, TNF, and the degranulation marker CD107a. A detailed description of this assay has been previously reported [43].

Soluble Factors/Serology

- Samples for soluble factor analysis will be collected as per Study Calendar. Sera and/or plasma may be analyzed pre- and post-therapy for changes in soluble factors (e.g. sCD27, sCD40L, sPD-1, sPD-L1), and cytokines (e.g. IFN- γ , IL-10, IL-12, IL-2, IL-4, etc.), chemokines, antibodies, tumor-associated antigens, and/or other markers using ELISA or multiplexed assays (e.g. Mesoscale, Luminex, cytokine bead array).
- Coded, linked samples will be sent to Quest for antibody analysis. The code will not be shared with Quest.

7.3.4.1 Additional assays:

- Blood samples may be used for additional research studies, which may include phenotypic and functional analysis of immune-cell subsets, and analyses for other cytokines (IFN- γ , IL-10, IL-12, IL-2, IL-4, etc.), chemokines, antibodies, and/or other markers. Additionally, blood samples may be used for whole or targeted high throughput genome sequencing on which bioinformatic analysis of immune system modulating genomic loci such as the IGHV region and the KIR region could be performed.

7.3.5 Summary of Correlative Samples for Vaccine-Naïve Cohorts

7.3.5.1 Collection of salivary and other blood specimens:

| Test/Assay | Volume blood** (approx) | Type of tube** | Collection point* | Location of specimen analysis |
|--|----------------------------|------------------------------|---|---|
| Salivary measurement of IgG antibodies | 1 mL (saliva) | Sarstedt 2.0 screw cap vials | D1, D29, D36, D57, D209 and D394 | NIH [name] Lab |
| Antigen Specific T cell Immune Response by cytokine staining assay | 60 mL (for PBMCs) | Sodium Heparin (Green top) | D1, D29, D36, D57, at COVID-19 infection*** | NIH Laboratory of Tumor Immunology and Biology (LTIB) |
| Standard and Refined immune cell subsets analysis by FACS | | Sodium Heparin (Green top) | D1, D29, D36, D57, at COVID-19 infection*** | NIH Laboratory of Tumor Immunology and Biology (LTIB) |
| Cytokines/soluble factors by ELISA/multiplexed assays | 8 mL (for serum) | SST | D1, D29, D36, D57, D209 and D394, at COVID-19 infection***. | NIH Laboratory of Tumor Immunology and Biology (LTIB) |

* See study calendar for collection windows. Sample collection should occur prior to vaccine administration on applicable days (i.e., D1 and D29). Participants who opt to receive a booster vaccine will have their samples drawn according to the Booster Vaccine Cohort calendar.

**Tubes/media may be adjusted at the time of collection based upon materials available if approved by the PI/laboratory investigator

***If a participant tests positive for COVID-19 while on study these labs will be collected within 2 weeks of a positive PCR test. A second post-infection blood collection will occur 2-4 weeks after this initial blood draw. These post-infection blood draws are optional.

7.3.6 Summary of Correlative Samples for Booster Vaccine Cohorts

7.3.6.1 Collection of salivary and other blood specimens:

| Test/Assay | Volume blood** (approx) | Type of tube** | Collection point* | Location of specimen analysis |
|--|----------------------------|------------------------------|---|---|
| Salivary measurement of IgG antibodies | 1 mL (saliva) | Sarstedt 2.0 screw cap vials | D1, 8*, 29, 57, 180, 360 | NIH [name] Lab |
| Antigen Specific T cell Immune Response by cytokine staining assay | 60 mL (for PBMCs) | Sodium Heparin (Green top) | D1, 8*, 29, 57, 180, 360, at COVID-19 infection***. | NIH Laboratory of Tumor Immunology and Biology (LTIB) |
| Standard and Refined immune cell subsets analysis by FACS | | Sodium Heparin (Green top) | D1, 8*, 29, 57, 180, 360, at COVID-19 infection***. | NIH Laboratory of Tumor Immunology and Biology (LTIB) |
| Cytokines/soluble factors by ELISA/multiplexed assays | 8 mL (for serum) | SST | D1, 8*, 29, 57, 180, 360, at COVID-19 infection***. | NIH Laboratory of Tumor Immunology and Biology (LTIB) |

* See study calendar for collection windows. Sample collection should occur prior to vaccine administration. D8 assessments are optional except for CAR T Cell Cohort.

**Tubes/media may be adjusted at the time of collection based upon materials available if approved by the PI/laboratory investigator

***If a participant tests positive for COVID-19 while on study these labs will be collected within 2 weeks of a positive PCR test. A second post-infection blood collection will occur 2-4 weeks after this initial blood draw. These post-infection blood draws are optional.

7.3.7 Future use of stored specimens

Samples will be ordered as appropriate (e.g., at NIH, ordered in CRIS and tracked through a Clinical Trial Data Management system; should a CRIS screen not be available, the CRIS downtime procedures will be followed). Samples will not be sent outside NIH without appropriate approvals and/or agreements, if required.

All specimens obtained in the protocol are used as defined in the protocol. Any specimens that are remaining at the completion of the protocol will be stored in the conditions described below. The study will remain open so long as sample or data analysis continues. Samples from consenting

subjects will be stored until they are no longer of scientific value or if a subject withdraws consent for their continued use, at which time they will be destroyed.

If the participant withdraws consent the participants data will be excluded from future distributions, but data that have already been distributed for approved research use will not be able to be retrieved.

The site PI will record any loss or unanticipated destruction of samples as a deviation. Reporting will be per the requirements of section **16.2.1**

On days samples are drawn, CSP (part of NCI Frederick Central Repositories) should be notified (phone: [name]; fax [name]). They will arrange same-day courier delivery of the specimens. All data associated with the participant samples is protected by using a secure database. All samples drawn at the NIH Clinical Center will be transported to the Clinical Support Laboratory at the Frederick National Laboratory for Cancer Research by couriers. Samples will be tracked and managed by Central Repository database, where there is no link to personal identifiable information. All samples will be stored in either a -80°C freezer or vapor phase liquid nitrogen. These freezers are located at NCI Frederick Central Repository in Frederick, Maryland. NCI Frederick Central Repositories (managed under a subcontract) store, among other things, biological specimens in support of NIH clinical studies. All specimens are stored in secure, limited-access facilities with sufficient security, backup, and emergency support capability and monitoring to ensure long-term integrity of the specimens for research. Specimens are stored in accordance with applicable HHS and FDA Protection of Human Subjects Regulations in accordance with the subcontractor's Federal-wide Assurance. The subcontractor's role limited to clinical research databases and repositories containing participant specimens. The subcontractor does not conduct or have any vested interest in research on human subjects but does provide services and support the efforts of its customers, many of which are involved in research on human subjects. The subcontractor's IRB reviews policies and procedures for labeling, data collection and storage, access, and security. The IRB will review protection of privacy issues prior to acceptance of any new work and in the event of change impacting privacy issues in existing work. It is the intent and purpose of the subcontractor to accept only coded, linked samples and sample information. To the limit of our ability, every effort will be made to ensure that protected information is not sent electronically or by hard copy or on vial labels. Sample data is stored in the BioSpecimen Inventory System II (BSI). This inventory tracking system is used to manage the

storage and retrieval of specimens as well as to maintain specimen data. BSI is designed for controlled, concurrent access. It provides a real-time, multi-user environment for tracking millions of specimens. The system controls how and in what order database updates and searches are performed. This control prevents deadlocks and race conditions. For security, BSI has user password access, 3 types of user access levels, and 36 user permissions (levels of access) that can be set to control access to the system functions. BSI provides audit tracking for processes that are done to specimens including shipping, returning to inventory, aliquoting, thawing, additives, and other processes. BSI tracks the ancestry of specimens as they are aliquoted, as well as discrepancies and discrepancy resolution for specimens received by the repository. If a specimen goes out of the inventory, the system maintains data associated with the withdrawal request. Vials are labeled with a unique BSI ID which is printed in both eye-readable and bar-coded format. No patient-specific information is encoded in this ID. Investigators are granted view, input, and withdrawal authority only for their specimens. They may not view specimen data or access specimens for which they have not been authorized. Access to specimen storage is confined to repository staff. Visitors to the repositories are escorted by repository staff at all times.

On days where saliva samples are collected, pre-labeled/barcoded 50 mL conical tubes containing ~3.0-5.0 mL of participant saliva and 3 pre-labeled/barcoded 2.0 mL screw-top flat bottom conical vials will be placed inside a sample biohazard bag placed inside another sample bag containing wet ice and couriered to OP-DEN. Once at OP-DEN receives the samples, please contact the Patient Care Coordinator (c: [contact]) by phone call or text, regarding the availability of the sample for pick up and processing. Samples will be processed in the OP-DEN clinical sample laboratory and aliquoted in 1.5-2.0 mL aliquots to be stored in a secure -80°C freezer in a locked cage.

8 ASSESSMENT OF SAFETY

8.1 Assessing and Recording Safety Parameters

Safety will be assessed by the frequency and severity of treatment related adverse events as defined by CTCAE V5, which is available here:

https://ctep.cancer.gov/protocoldevelopment/electronic_applications/docs/ctcae_v5_quick_reference_5x7.pdf

The CTCAE utilizes the System Organ Class (SOC) terminology derived from MedDRA in order to organize the adverse events into appropriate sections. SOC reflects the highest level of the MedDRA1 hierarchy. Each SOC is identified by an anatomical or physiological system, an etiology, or a purpose (e.g., SOC Investigations for laboratory test results). CTCAE terms are grouped by MedDRA Primary SOCs. Within each SOC, AEs are listed and accompanied by descriptions of severity (Grade).

If the CTCAE V5 does not have the required term, investigators are encouraged to consult MedDRA (<https://www.meddra.org/>) in order to utilize the appropriate MedDRA term. Within each SOC, the final adverse event term allows for a free text “Other” term. If investigators are unable to find a specific term describing the adverse event within CTCAE, investigators should utilize the free text “Other” terminology and report the appropriate MedDRA term. This will enable appropriate comparisons of with the mRNA-1273 Phase 3 trial, which utilized MedDRA.

8.1.1 Adverse Events (AEs)

ICH E6 defines an AE as any untoward medical occurrence in a participant or clinical investigation Participant administered a pharmaceutical product regardless of its causal relationship to the study treatment. FDA defines an AE as any untoward medical occurrence associated with the use of a drug in humans, whether or not considered drug related.

An AE can therefore be any unfavorable and unintended sign (including an abnormal laboratory finding), symptom, or disease temporally associated with the use of medicinal (investigational) product. The occurrence of an AE may come to the attention of study personnel during study visits and interviews of a study recipient presenting for medical care, or upon review by a study monitor.

All AEs, including solicited local (injection site) and systemic (subjective and quantitative) reactions, will be captured on the appropriate data collection form and eCRF. Information to be collected for AEs includes event description, date of onset, assessment of severity, relationship to study product and alternate etiology (assessed only by those with the training and authority to make a diagnosis and listed on the Form FDA 1572 as an investigator), date of resolution, seriousness and outcome. AEs occurring during the trial collection and reporting period will be documented appropriately regardless of relationship. AEs will be followed through resolution.

Any medical condition that is present at the time that the Participant is screened will be considered as baseline and not reported as an AE. However, if the severity of any pre-existing medical condition increases, it should be recorded as an AE.

If an event meets both the criteria of a study endpoint and an adverse event, the event will be reported either as a study endpoint or as an adverse event (not both).

8.1.1.1 Adverse Events Grading

All AEs (laboratory and clinical symptoms) will be graded for severity and assessed for relationship to study product (see definitions). AEs characterized as intermittent require documentation of onset and duration of each episode. The start and stop date of each reported AE will be recorded on the appropriate data collection form and eCRF. Changes in the severity of an AE will be documented to allow an assessment of the duration of the event at each level of intensity.

8.1.1.1.1 Severity of Event:

The severity of unsolicited AEs will be assessed by the investigator using the NCI Common Terminology Criteria for Adverse Events (NCI-CTCAE) version 5.0.

The severity of solicited AEs will be assessed by the investigator using the clinical abnormalities section of the FDA "[Toxicity Grading Scale for Healthy Adult and Adolescent Volunteers Enrolled in Preventive Vaccine Clinical Trials](#)".

The following grading system utilized for the events not listed in the above scales:

- * Mild (Grade 1): Events that are usually transient and may require only minimal or no treatment or therapeutic intervention and generally do not interfere with the Participant's usual activities of daily living.
 - Transient: Duration less than 48 hours

- Therapeutic Intervention: An action to alleviate the adverse event that does not require a medication or medical procedure, such as a change in diet, or application of cool pack or warm compress, or rest
- * Moderate (Grade 2): Events that are usually alleviated with additional specific therapeutic intervention. The event interferes with usual activities of daily living, causing discomfort but poses no significant or permanent risk of harm to the research participant.
- Therapeutic Intervention: Use of non-narcotic pain reliever or over-the-counter medication
- * Severe (Grade 3): Events interrupt usual activities of daily living, or significantly affects clinical status, or may require intensive therapeutic intervention. Severe events are usually incapacitating.
- Activities of Daily Living (ADLs): Negative impact on ADLs, such as missed work, unable to do housework or exercise
- Significantly Affects Clinical Status: A medically attended event – clinical care was sought from a healthcare professional
- Intensive Therapeutic Intervention: Required prescription medication, or intravenous fluids or medical procedure

8.1.1.2 Relationship to Study Product:

The assessment of the AE's relationship to study product will be done by the licensed study physician indicated on the Form FDA 1572 and the assessment will be part of the documentation process. Whether the AE is related or not, is not a factor in determining what is or is not reported in this trial. If there is any doubt as to whether a clinical observation is an AE, the event should be reported.

In a clinical trial, the study product must always be suspect. The relationship to study product will be assessed for AEs using the terms related or not related:

- * Related – There is a reasonable possibility that the study product caused the AE. Reasonable possibility means that there is evidence to suggest a causal relationship between the study product and the AE.
- * Not Related – There is not a reasonable possibility that the administration of the study product caused the event.

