11.4.2.2 Safety Analyses

Safety and reactogenicity will be assessed by clinical review of all relevant parameters including solicited ARs (local and systemic events), unsolicited AEs, SAEs, AEs leading to discontinuation, safety laboratory test results, vital signs, and physical examination findings.

Solicited ARs and unsolicited AEs will be coded by system organ class (SOC) and preferred term according to the MedDRA for adverse reaction terminology. The Toxicity Grading Scale for Healthy Adult and Adolescent Volunteers Enrolled in Preventative Vaccine Clinical Trials (DHHS 2007) is used in this study with modification for rash, solicited ARs, unsolicited AEs, and vital signs.

Rash will be graded as:

- Grade 0 = no rash
- Grade 1 = localized without associated symptoms
- Grade 2 = maculopapular rash covering $< 50\%$ body surface area
- Grade 3 = urticarial rash covering $> 50\%$ body surface area
- Grade 4 = generalized exfoliative, ulcerative or bullous dermatitis

All safety analyses will be based on the Safety Set, except summaries of solicited ARs which will be based on the Solicited Safety Set. All safety analyses will be provided overall and by cohort.

The number and percentage of participants with any solicited local AR, with any solicited systemic AR and with any solicited AR during the 7-day follow-up period after each injection will be provided with a 2-sided 95% exact CI using the Clopper-Pearson method.

Number and percentage of participants with unsolicited AEs, SAEs, Grade 3 or higher ARs and AEs, treatment-related AEs and SAEs, and AEs leading to discontinuation from study vaccine or participation in the study will be summarized. Unsolicited AEs will be summarized by system organ class and/or preferred term coded by MedDRA.

For treatment-emergent safety laboratory tests results, the raw values and change from baseline values will be summarized by timepoint.

The number and percentage of participants who have chemistry, hematology, coagulation, and vital signs results below or above the laboratory normal ranges will be tabulated by timepoint.

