| Hypotension (systolic) – mm Hg | 85 - 89 | 80 - 84 | < 80 | ER visit or hospitalization for hypotensive shock |
| Respiratory Rate – breaths per minute | 17 - 20 | 21 – 25 | > 25 | Intubation |

* Participant should be at rest for all vital sign measurements.

** Oral temperature; no recent hot or cold beverages or smoking.

*** When resting heart rate is between 60 – 100 beats per minute. Use clinical judgement when characterizing bradycardia among some healthy participant populations, for example, conditioned athletes.

| Systemic (General) | Mild (Grade 1) | Moderate (Grade 2) | Severe (Grade 3) | Potentially Life Threatening (Grade 4) |
|--|--|--|--|---|
| Nausea/vomiting | No interference with activity or 1 – 2 episodes/24 hours | Some interference with activity or > 2 episodes/24 hours | Prevents daily activity, requires outpatient IV hydration | ER visit or hospitalization for hypotensive shock |
| Diarrhea | 2 – 3 loose stools or < 400 gms/24 hours | 4 – 5 stools or 400 – 800 gms/24 hours | 6 or more watery stools or > 800gms/24 hours or requires outpatient IV hydration | ER visit or hospitalization |
| Headache | No interference with activity | Repeated use of non-narcotic pain reliever > 24 hours or some interference with activity | Significant; any use of narcotic pain reliever or prevents daily activity | ER visit or hospitalization |
| Fatigue | No interference with activity | Some interference with activity | Significant; prevents daily activity | ER visit or hospitalization |
| Myalgia | No interference with activity | Some interference with activity | Significant; prevents daily activity | ER visit or hospitalization |
| Illness or clinical adverse event (as defined according to applicable regulations) | No interference with activity | Some interference with activity not requiring medical intervention | Prevents daily activity and requires medical intervention | ER visit or hospitalization |

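### Solicited chills and arthralgia have no row in Appendix D, and the routes left for grading them set different Grade 3 thresholds, so the Grade 3 or higher summary is inconsistent and may be inflated

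*Combined protocol and SAP*

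**What the plan says.** Section 8.1.1.1.1 assigns CTCAE v5 to unsolicited events and the FDA vaccine toxicity scale to solicited ones. It then adds a third scale: "The following grading system utilized for the events not listed in the above scales". This fallback has three levels. Its top level reads "Severe (Grade 3): Events interrupt usual activities of daily living, or significantly affects clinical status, or may require intensive therapeutic intervention". The sub-definitions explain the terms:

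- effect on daily living: "Negative impact on ADLs, such as missed work, unable to do housework or exercise"
- effect on clinical status: "A medically attended event – clinical care was sought from a healthcare professional"
- treatment: "Intensive Therapeutic Intervention: Required prescription medication, or intravenous fluids or medical procedure"

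Section 8.1.2 lists 11 solicited reactions, including chills and arthralgia. Section 2.5.1 expects both to be among the most common systemic reactions. Appendix D, which says it governs reactogenicity grading, has a row for each of the other nine but none for these two. It does have a general row for an illness or clinical adverse event, graded 1 to 4, where Grade 3 is "Prevents daily activity and requires medical intervention". The myalgia and fatigue rows use interference with activity alone for Grades 1 to 3, and an emergency visit or hospitalization for Grade 4.

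For unsolicited events, section 8.1 sends the investigator to a free-text Other entry: "If investigators are unable to find a specific term describing the adverse event within CTCAE". Section 11.4.2.2 says that the modified DHHS 2007 vaccine scale is used for unsolicited events too, and plans a summary of "Grade 3 or higher ARs and AEs".

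**The concern.** Chills, arthralgia, myalgia and fatigue are similar reactions and go into the same Grade 3 or higher summary. If two of them are graded on another rule, that summary mixes thresholds. The fallback rule is the lower one, because a healthcare contact or a required prescription is sufficient whatever the effect on activity. Participants have cancer and many are on active treatment, so contact with a clinician is a weak marker of how severe a reaction was.

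Safety results are reported by cohort as well as overall, and the cohorts have 10 to 30 participants (section 11.2). One or two participants graded differently would be visible in a cohort table. Two investigators could also grade the same event differently and both be following the protocol.

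**Working it through.** The documents give no expected Grade 3 rate and no precision target, so there is no figure to reproduce. Three checks apply.

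**1. The three wordings side by side.** Describe an event by its effect on activity (none, some, prevented), whether care was sought, whether a prescription was required, and whether there was an emergency visit or hospitalization. Such a visit implies that care was sought. This leaves 6 care patterns for each of 3 activity levels, so 3 × 6 = 18 profiles. Care sought or a prescription is taken as medical intervention in the general row. Some interference without care is taken as Grade 2 on the fallback.

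| Activity | Care pattern | Profiles | Fallback | General row | Myalgia/fatigue rows |
|---|---|---|---|---|---|
| None | Neither care nor prescription | 1 | 1 | 1 | 1 |
| None | Care, prescription or both | 3 | 3 | 1 | 1 |
| Some | Neither | 1 | 2 | 2 | 2 |
| Some | Care, prescription or both | 3 | 3 | not placed | 2 |
| Prevented | Neither | 1 | 3 | not placed | 3 |
| Prevented | Care, prescription or both | 3 | 3 | 3 | 3 |
| Any | Emergency visit or hospitalization | 6 | 3 | 4 | 4 |

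Profiles at Grade 3 or higher:

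- fallback: 3 + 3 + 1 + 3 + 6 = 16 of 18
- general row: 3 + 6 = 9 of 18, with 3 + 1 = 4 profiles that its wording does not place
- myalgia and fatigue rows: 1 + 3 + 6 = 10 of 18, with every profile placed

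No profile is Grade 3 or higher on the other two wordings and lower on the fallback, so the fallback can only push the count up. Six profiles are Grade 3 on the fallback but Grade 1 or 2 on the myalgia wording. For example, arthralgia that needs a prescription but does not interfere with activity is Grade 3 on the fallback and Grade 1 on either Appendix D wording. The counts are not weighted by how often each profile occurs, so they give the direction and not the size.

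**2. Does stopping at Grade 3 matter to the planned summary?** For any grade g, min(g, 3) ≥ 3 exactly when g ≥ 3. With example grades 1, 1, 2, 3, 3, 4, 4, 5, the number at Grade 3 or higher is 5 with or without the cap. The number at Grade 4 or higher is 3 without it and 0 with it. Only the breakdown above Grade 3 is lost.

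**3. Scale in a cohort.** Assume that no participant has a Grade 3 event on the myalgia wording, and that 1 to 3 are upgraded only because of a contact or a prescription. Both numbers are assumptions. The exact (Clopper-Pearson) limits are the 0.025 quantile of Beta(x, n − x + 1) and the 0.975 quantile of Beta(x + 1, n − x). For 0/20 the upper limit is 1 − 0.025^(1/20) = 16.8%.

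| n | 0 upgraded | 1 | 2 | 3 |
|---|---|---|---|---|
| 20 | 0% (0–16.8) | 5.0% (0.1–24.9) | 10.0% (1.2–31.7) | 15.0% (3.2–37.9) |
| 30 | 0% (0–11.6) | 3.3% (0.1–17.2) | 6.7% (0.8–22.1) | 10.0% (2.1–26.5) |
| 220 | 0% (0–1.7) | 0.5% (0.0–2.5) | 0.9% (0.1–3.2) | 1.4% (0.3–3.9) |

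Section 11.4.2.2 plans only number and percentage for the Grade 3 or higher summary. The intervals are added here to show scale.

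**The case against.** The strongest reply is that the fallback may hardly be used. Appendix D claims all reactogenicity grading, and its general row can be read as covering chills and arthralgia. The fallback applies only to events in neither named scale, and whether CTCAE v5 lists these two terms cannot be checked from the documents. For unsolicited events, the CTCAE Other entry leaves little for the fallback to catch. All of this stands, so inflation is possible but not shown. It does not remove the point, because no sentence selects the general row. That row also differs from the myalgia and fatigue rows and leaves some profiles without a grade.

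A second reply is that little depends on the count, which also stands. The primary safety endpoints in section 3.2 are not defined by grade, the halting rules in section 8.9.1 do not use grade, and section 11.1 rules out hypothesis testing. The summary counts participants, so someone already at Grade 3 for another reaction adds nothing.

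A reader might go further and infer that Grade 3 or higher counts are wrong in both directions because the fallback has no Grade 4 or 5. The second check shows otherwise: a capped event is still counted. Deaths and life-threatening events are also captured as serious adverse events (section 8.1.3) and summarised separately. A reader might also infer that the table of any solicited reaction is distorted. It is not, because grade does not enter that table.

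The overlap between the fallback's Grades 2 and 3 on daily activities is real but partial. The Grade 3 examples are stronger, and the text describes severe events as usually incapacitating.

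**Conclusion.** The point holds as an unresolved grading rule. The text leaves two routes for chills and arthralgia, and neither sets the Grade 3 threshold used for myalgia and fatigue. By either route, the Grade 3 or higher summary treats similar reactions differently. If the fallback is the route taken, the error can only be upward: 16 of 18 profiles against 10 on the myalgia wording. How many participants that means cannot be derived from the documents, and the cohort figures above rest on an assumed 1 to 3 upgrades.

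A related conflict is plain from the text. Section 8.1.1.1.1 gives unsolicited events to CTCAE v5, while section 11.4.2.2 applies the modified DHHS 2007 scale to them.

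The documents do not support saying that the counts are wrong, or that the fallback definitely governs these two reactions. The point is minor to moderate and is confined to descriptive safety tables.

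**What to change.** 1. Add chills and arthralgia to Appendix D with the functional wording already used for myalgia and fatigue.
2. Reconcile sections 8.1, 8.1.1.1.1 and 11.4.2.2 so that one scale is named for each event type.
3. Remove the three-level fallback. Grade unlisted unsolicited events under the CTCAE v5 Other entry. Section 8.1 already directs their naming there, but should also say that their severity is graded on CTCAE v5.
4. Record medical attendance as a separate yes/no item, so that the information is kept without acting as a severity grade.

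The cost is protocol wording, an eCRF note, and regrading of any events already graded on the fallback. Section 7.1.4 says that the memory aids are destroyed, so regrading will work only where the source record shows the effect on activity and any emergency visit or hospitalization. That should be checked first. Where the record falls short, the affected events should be footnoted in the Grade 3 or higher table.
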